A Prospective Study of Bone Augmentation in Extraction Sockets
and Implant Surface Textures.

Study Protocol & Statistical Analysis Plan

NCT00641316

September 17, 2021

[name], MS, Principal Investigator

University of Alabama at Birmingham
Birmingham, Al 35294

Study Synopsis

Study Title	A Prospective Study of Bone Augmentation in Extraction Sockets and Implant Surface Textures.
Rationale	
Tooth extraction is often associated with resorption of alveolar ridge height and width and with compromised soft tissue contours. An increasingly common periodontal practice combines skilled surgical technique with extraction site grafting. These procedures are thought to retard resorption of the socket volume while lending some control over bone-fill – thereby preserving the integrity of the alveolar ridge for future reconstruction with dental implants.
 
While limited evidence-based data exist to support this premise, conflicting data suggest that the grafting materials may, in fact, impede natural post-extraction healing.
 
In addition, the prevailing recommendation to allow grafted bone to heal for four to six months before contemplating reconstruction with dental implants is also under scrutiny and is cause for debate. Clearly, additional investigation is warranted.
 
In an effort to establish clinical evidence this randomized-controlled clinical trial will assess and compare the efficacy of three different bone grafting applications. After two months results will be compared to a control group where sites that have been allowed to heal without grafting intervention.
 
The study will then assess the efficacy of early reconstruction with two-piece dental implants. We will evaluate the effects of two implant collar surface topographies on the longitudinal maintenance of peri-implant osseous and soft-tissue health. Follow-up evaluations will be completed at 12 and 24 months after placement of the implants.

Objectives	
To evaluate hard and soft tissue healing of grafted and non-grafted extraction sockets in the aesthetic zone.
 
To evaluate longitudinal clinical outcome of dental implants with differing collar surfaces implanted in sites 8 weeks after tooth extraction.

Hypotheses	
Hypothesis I Bone grafted sites preserve alveolar ridge dimensions of extraction sockets more effectively than extraction sites that have healed without grafting.
 
Hypothesis II The addition of growth factors to bone grafting materials will enhance osseous and soft-tissue healing.
 
Hypothesis III Laser Thread Textured (LTT) dental implant will preserve longitudinal peri-implant crestal bone more effectively than implants with a Resorbable Blast Textured (RBT) surface.

Randomization	
Participants will be stratified for smoking status and randomized to one of four extraction protocol groups and one of two implant groups:
 
Extraction Groups:
 
 Group 1. Atraumatic extractions followed by saline irrigation and natural healing [Control] Group 2. Atraumatic extractions followed by Freeze-Dried Bone Allograft (FDBA) Tri-Calcium Phosphate (TCP) + collaplug Group 3. Atraumatic extractions followed by FDBA/TCP/Platelet-Rich Plasma (PRP) +collaplug Group 4. Atraumatic extractions followed by FDBA/TCP/Platelet-Derived Growth Factors (PDGF) + collaplug 
A secondary randomization will be conducted to select one tooth site per subject to receive trephine sampling for histology evaluation.
 
Implant Groups:
 
 Group-A. LTT collar surface topography Group-B. RBT collar surface topography
Procedures	
Extractions
 
Atraumatic extractions and graft/no-graft procedures will be completed following the randomization table and standardized surgical procedures. Three-dimensional images, acquired through Cone-Beam CAT-Scan (CBCT), will be captured immediately post-extraction. Prophylactic antibiotics will be dispensed, prescriptions for post-surgery antibiotics and analgesics (prn) will be written. Antibacterial mouth wash will be dispensed; written and verbal patient home-care instructions will be provided
 
To preserve anterior aesthetics, during the healing phase, an Essix retainer will be made for each participant and inserted immediately after the extractions/grafting procedures.
 
Follow-up evaluations
 
Performed at week-1, week-2 and week-4, will include:
 
 Assessment of adverse experiences Measurement of clinical parameters Clinical photographs Suture removal at week 2 
Implant Placement
 
A clinical evaluation and surgical placement of implants completed at week-8 – to include:
 
 CBCT scan Prophylactic antibiotics dispensed Pre-surgical oral rinse Measurement of clinical parameters

	
Clinical photographs One bone-fill specimen per patient, harvested by trephine (placed in fixative for later histological analysis)
 
Surgeon's subjective observation of osseous fill quality (D-1-D-4) Randomized insertion of one, two-piece, dental implant per study site Immediate post-surgical intra-oral radiographs Prescriptions for post-surgery antibiotics and analgesics (prn) Antibacterial mouth wash and ice-packs dispensed Written and verbal home-care instructions
 
Post- Insertion Follow-up Implant surgical follow-up assessment and suture removal will be performed after two-weeks.
 
Implants Uncovered Mandibular implants will be uncovered after approximately 4 months; maxillary implants will be uncovered after approximately 6 months.
 
Implant Restoration Implants will be restored in the conventional manner with aesthetically pleasing cemented single crown restorations.
 
Longitudinal Follow-up Two annual follow-up evaluations will be completed at 12 months and 24 months after surgical implant placement. Each assessment will include:
 
Standardized intra-oral periapical dental radiographs Clinical photographs Measurement of clinical parameters Assessment of soft-tissue contours Assessment of overall aesthetics Assessment of implant/restoration interface Patient satisfaction survey

Population	
Eighty healthy adult patients (20 in each extraction group) of any ethnicity or gender whose treatment plan includes extraction of mandibular and/or maxillary pre-molars and/or maxillary anterior teeth and their replacement with root-form dental implants will be consecutively recruited for enrollment in the study.
 
Only treatment of non-adjacent sites will be included in the database. Each participant may have up to four non-adjacent sites selected for inclusion as study treatment sites.
 
Participants must be 19 years old or older with demonstrated ability to understand the proposed treatment recommendations and prognosis and be able to provide informed consent, in English, without the aid of ad hoc translation.

	
Participants with a reported history of a previous malignant neoplasm, a known hypersensitivity to β-TCP or rhPDGF-BB, a Titanium metal allergy, or any other health condition or medication regimen that, in the opinion of the investigators, may adversely affect bone healing will be excluded.
 
Women who are pregnant or nursing at the time of recruiting will be excluded.

Outcomes	
Radiographic image analysis of osseous architecture changes at study sites over time
 
Soft-Tissue aesthetic assessments
 
Patient Satisfaction assessments
 
Data analysis – results and conclusions
 
Final report

Statistical Analyses	
The general approach to statistical analysis of the study aims will be based on mixed-model analysis of variance (ANOVA). This approach will accommodate the inclusion of correlated observations due to study subjects potentially contributing measurements of more than one single tooth site to the analysis.
 
The sample distributions will be examined for each outcome variable. If these distributions depart substantially from normality, transformations of the data will be evaluated. If normality cannot be established by transformation, rank-based analyses will be used.
 
Subjects will be included as a random effect on the analyses that include multiple observations per subject. For analysis of histological data, only one tooth site per subject will be evaluated and the model will not include a random effect.
 
Smoking status will be included in all models so that the analysis will correspond to the study's randomization strategy.
 
For the aims in which interaction terms are of interest, significant interaction terms will be investigated using plots of least-square means and separate post-hoc analyses for individual time points.

Table of Contents

Section	Title	Page
1:	Background and Significance	6
2:	Investigational Design	9
3:	Study Population	10
4:	Study Procedures	11
5:	Tissue Biopsy & Surgical Implant Placement	15
6:	Restoration of Implants	17
7:	Longitudinal Follow-up Protocol	17
8:	Radiographic & Photographic Surveys	18
9:	Adverse Event Reporting	19
10:	Criteria for Success	19
11:	Costs to Participants	20
12:	Outcomes and Analyses	21
13:	Confidentiality	25
14:	Regulatory Issues	26
15:	Ethical Issues	27
16:	Literature Cited	28
17	Study Personnel	31
18	Signature Page	32

Appendices

A:	FDA 510(k) Device Approval
B	Safety and Effectiveness – GEM-21S™
C:	Informed Consent

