4.7 Grafting Extraction Sockets

After extractions, sockets will be grafted according to each participant's assigned randomization group.

Group-1: Each socket will be irrigated with sterile saline and allowed to heal naturally [control group].

Group-2: Each socket will be grafted with freeze dried bone allograft (FDBA) mixed with Tri-calcium phosphate (TCP) 8:2 ratio; reconstituted with sterile saline.

4.7-2a Irrigate sockets with sterile saline

4.7-2b Pack the graft into each of the study sites using mild pressure achieving complete fill of the sockets.

4.7-2c Trim a 3mm section of collaplug and secure it over the grafted areas with 4.0 Vicryl crossing mattress sutures.

Group 3: Each socket will be grafted with an 8:2 ratio FDBA/TCP graft reconstituted with Platelet Rich Plasma (PRP).

4.7-3a Collect 9-18cc blood sample from the patient via venipuncture prepare the PRP following the Cascade Fibrinet System (Appendix A)

4.7-3b Mix PRP in the FDBA.TCP graft.

4.7-3c Irrigate sockets with sterile saline.

4.7-3d Pack the graft into each of the study sites using mild pressure achieving complete fill of the sockets

4.7-3e Trim a 3mm section of collaplug and secured it over the grafted areas with 4.0 Vicryl crossing mattress sutures.

4.7-3f Once secured in place, the soak the collaplug with PRP.

Group 4: Each socket will be grafted with an 8:2 ratio FDBA/TCP graft reconstituted with recombinant platelet derived growth factor (PDGF).

4.7-4a Irrigate sockets with sterile saline.

4.7-4b Apply PDGF into the sockets completely wetting all socket walls.

4.7-4c Mix PDGF with GEM-21S (product insert Appendix B)

4.7-4d Pack the graft into each of the study sites using mild pressure achieving complete fill of the sockets

4.7-4e Trim a 3mm section of collaplug and secure it over the grafted areas with 4.0 Vicryl crossing mattress sutures.

4.7-4f Once secured in place, soak the collaplug with PDGF.

After completion of procedures the Essix retainer (if used) will be fitted and placed.

A CBCT scan will be made to include images of each study site. Prescriptions for anti-bacterial mouth wash, antibiotics, and pain relief will be provided based on individual patient needs. An ice-pack will be dispensed. Verbal and written home care instructions will be given and the patient will be scheduled for a follow-up appointment.

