12.4 Statistical Analysis

The general approach to statistical analysis of the study aims will be based on mixed-model analysis of variance (ANOVA). This approach will accommodate the inclusion of correlated observations due to study subjects potentially contributing measurements of more than one single tooth site to the analysis.

The sample distributions will be examined for each outcome variable. If these distributions depart substantially from normality, transformations of the data will be evaluated. If normality cannot be established by transformation, rank-based analyses will be used.

Subjects will be included as a random effect on the analyses that include multiple observations per subject. For analysis of histological data, only one tooth site per subject will be evaluated and the model will not include a random effect.

Smoking status will be included in all models in order to account for differences in response between smokers and non-smokers, and so that the analysis will correspond to the study's randomization strategy. Comparisons between smokers and non-smokers are not a primary interest in the study.

For aims in which interaction terms are of interest, significant interaction terms will be investigated using plots of least square means and separate post-hoc analyses for individual time points.

Hypothesis 1

Differences among the four groups will be evaluated by the overall F-test for the ANOVA. Pairwise comparisons among group means will be conducted using Tukey's test. Contrasts will be constructed to address each specific aim (SA).

SA-1: Compare alveolar ridge dimensions in grafted extraction sockets to that of sites healed without grafts after 8 weeks of post-extraction healing.

This SA will be addressed by comparing the combined mean of the three graft groups (FDBA/TCP, DDBA/TCP/PRP, FDBA/TCP/PDGF) with that of the CONTROL group by calculating a contrast and the corresponding F-test. Pairwise comparisons among means will be conducted using Tukey's test..

Hypothesis II

The addition of growth factors to bone grafting materials will enhance osseous and soft tissue healing.

SA-2: Assess the efficacy of bone grafting with and without enrichment with growth factors to preserve the volume of bone in extraction sockets.

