A conservative approach to power estimation was used, assuming an effective sample size of 25 observations per extraction-implant group. Power calculations utilized the Power and Precision, release 2.00, (Borenstein, 2000) and nQuery Advisor 6.0 (Janet D. Elashoff, 1995-2005) software packages. Power to detect a “medium” effect size, corresponding to a difference between group means equal to 0.50 times the within-group standard deviation (sd) was calculated. Also, the effect size detectable with 80% power was calculated. All power estimates were based on two-sided testing at the 95% confidence level.

The power for SA-1 is largely determined by the size of control group, since the primary comparison is equivalent to a t-test of the mean of the controls vs others. Thus, the assumed effective sample sizes of 25 and 75 would yield approximatey 57% power to detect a medium effect size. The difference detectable with 80% power would be approximately 0.65sd .

Power for SA-2, SA-4 and SA-5 was based on a one-way ANOVA model. The proposed sample size would provide 52% power to detect a medium effect size or 80% power to detect an effect size equivalent to a two-group difference of 0.34sd . These approximations also apply to SA-3, with the appropriate sd being the within-group standard deviation of the changes across the observation times.

The total sample size for SA-5 would be 80, or 20 per group, since this SA is based on histology, with a single extraction per participant. Power to detect a medium effect size would be 42%. The effect size detectable with 80% power is equivalent to a two-group difference of 0.72sd.

Power for SA-6 was based on linear regression with a four-category dummy variable. If stability and group each explain 10% of the observed variance, the proposed sample size would provide 80% power to detect an increment of 8.6% in explained variance for the stability*group interaction.

Power for comparison of rates of infection signs for SA-7 was based on the chi-square test for the odds ratio. The proportions in the two groups were centered on 0.50, in order to provide a conservative estimate of power. The effective sample size of 50 per group would provide 80% power to detect an odds ratio of approximately 3.2 for the association between implant type and infection.

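### SA-1 tests one control group against three pooled graft groups with a single error variance; a prespecified unequal-variance contrast would protect its 5% level at a cost of about one point of power

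*Combined protocol and SAP*

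**What the plan says.** The synopsis and section 12.4 give the same general rule: "The general approach to statistical analysis of the study aims will be based on mixed-model analysis of variance (ANOVA"), with subject as a random effect where a participant contributes several sites. The distributional safeguards concern shape only. "If these distributions depart substantially from normality, transformations of the data will be evaluated", and then: "If normality cannot be established by transformation, rank-based analyses will be used". Nowhere does the text mention homogeneity of variance, variances by group, Welch or Satterthwaite methods, or robust standard errors.

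For SA-1, the only aim under Hypothesis I, section 12.4 plans "comparing the combined mean of the three graft groups (FDBA/TCP, DDBA/TCP/PRP, FDBA/TCP/PDGF) with that of the CONTROL group", using a contrast and its F-test, with Tukey's test for pairs. Section 12.5 treats this as a two-sample problem: "the primary comparison is equivalent to a t-test of the mean of the controls vs others". It assumes effective sizes of 25 and 75 and one within-group SD, and reports 57% power for a difference of 0.50 SD and a detectable difference of about 0.65 SD.

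Section 3.1 sets 20 participants per group. Under section 4.7 Group 1 is irrigated and left to heal, while the instruction for Groups 2-4 is: "Pack the graft into each of the study sites using mild pressure achieving complete fill of the sockets". For SA-5, percent new bone, residual graft and soft tissue are compared among all four groups by ANOVA and Tukey's test.

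**The concern.** A common error variance is not written out in the plan, but it is the default of every method named (ANOVA F-test, Tukey, t-test power with one SD), and no alternative is offered. Pooled-variance tests tolerate unequal SDs well when two groups of equal size are compared. SA-1 is not that comparison, because its weights are 1 against 1/3, 1/3, 1/3.

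If ungrafted sockets vary more than grafted ones, the error term is too small and the test rejects a true null of equal means too often. If they vary less, the error term is too large and power is lost. The confidence interval for the grafting effect is too narrow or too wide in the same way. Neither case triggers a change of analysis under the plan.

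**Working it through.** **Inputs.** Four equal arms (section 3.1). Effective n of 25 per arm, so 25 v 75; two-sided 5%; effect 0.50 SD (section 12.5). ICC 0.50 and 1.5 sites per participant (section 12.5). The control:graft SD ratio r is an assumption, shown as a range, because the documents give no SD by arm. Smoking status was left out of the simulations.

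**1. The plan's own figure.** Noncentrality = 0.50 / √(1/25 + 1/75) = 0.50 / 0.2309 = 2.165. On 98 df, two-sided 5%, power is 57.3%. The difference detectable with 80% power is 0.653 SD. Both stated figures reproduce.

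**2. Why equal arms do not help.** Let the control SD be r, the graft SD 1, and n the size of each arm.
- True variance of the contrast: (r² + 1/3)/n.
- Variance that the pooled error estimates: (r²/3 + 1)/n.
- Ratio: R = (r² + 1/3)/(r²/3 + 1), which equals 1 only at r = 1.
- Large-sample type I error: 2Φ(−1.96/√R).

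Example, r = 1.5: R = 2.583/1.750 = 1.476; 1.96/√1.476 = 1.613; type I error 10.7%.

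| SD ratio r | R | Formula | Simulated, pooled (n = 25 per arm) |
|---|---|---|---|
| 0.67 | 0.677 | 1.7% | 1.9% |
| 1 | 1.000 | 5.0% | 5.0% |
| 1.25 | 1.247 | 7.9% | 7.9% |
| 1.5 | 1.476 | 10.7% | 10.5% |
| 2 | 1.857 | 15.0% | 14.9% |

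The same contrast with separate variances and Satterthwaite df has a simulated error of about 5% throughout.

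**3. Does clustering or the rank fallback change this?** No. A random-intercept model with common variances (80 participants, 1.5 sites on average, ICC 0.50) gives 1.7% / 5.0% / 8.1% / 11.1% / 15.4% at the five ratios. A rank-transformed contrast gives 2.9% / 4.7% / 7.8% / 10.0% at ratios 0.67 / 1 / 1.5 / 2, so it reduces the problem without removing it.

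**4. Where the problem does not extend.** The overall four-group F-test has 5.3% to 5.7% error at unequal ratios between 0.5 and 1.5, and 6.4% at 2. Tukey's familywise error with equal arms is 5.0% to 5.8% for ratios 0.5 to 1.5, and about 6.8% at 2.

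**5. Which remedy works.** At ICC 0.50 half of the variance lies between subjects. Letting only the residual variance differ by group leaves that half common: a simulation of 1,500 runs gave 3.0% / 6.5% / 6.7% at ratios 0.67 / 1.5 / 2. With the subject variance also differing by group it was 4.5% to 5.1%. A Welch-type contrast on participant means gave 5.1% to 5.4%, and 4.9% to 5.1% in a larger run.

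**6. Cost.** With equal SDs and a 0.50 SD difference, power is about 57% pooled and 56% with separate variances. At r = 0.67 and a difference of 0.50 graft SD, it is 67% pooled and 80% separate.

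**7. SA-5, percent residual graft.** Group 1 receives no graft, so its values should be zero or nearly so. With control variance 0 and graft variance s², the pooled error is (0 + 3s²)/4 = 0.75s², a quarter too small for comparing graft arms. With n = 20 per group, the simulated error of an unadjusted graft-pair test is 9.1%. Tukey's familywise error among the three graft arms is 6.6%, against 2.9% with the correct error term.

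**The case against.** The strongest reply is that nothing in the documents shows unequal variances for ridge dimensions. That stands: at a ratio of 1 the test is exact, and the documents do not say in which direction any departure would go. A reader might infer that the 5% level is wrong whichever way the variances fall. The documents do not support that.

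A reader might also take the packing instruction in section 4.7 as evidence of different spread. It describes socket contents on the day of surgery, whereas the SA-1 outcome is ridge dimensions at 8 weeks. Anatomical variation shared across arms would pull the ratio towards 1. As an illustration only (the shared fraction is not in the documents), take a treatment-related ratio of 1.5. With half of the graft-arm variance shared, the overall ratio is √(0.5 + 0.5 × 2.25) = 1.27, with an error of about 8.1%. With three quarters shared, it is √(0.75 + 0.25 × 2.25) = 1.15, with 6.7%. So the 10% to 15% figures are the upper end.

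Inflation also requires a null in which grafting alters the spread but not the mean. If grafting does nothing at all, the arms share one distribution. This narrows the type I error claim, but not the points about power and interval width.

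Finally, one might infer that every Tukey comparison should be replaced by Games-Howell. Step 4 does not support that. None of these replies supplies a safeguard for SA-1.

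**Conclusion.** The point holds as a cheap, conditional improvement to SA-1. If the control:graft SD ratio lay between 0.67 and 2, the type I error of the planned contrast would lie between about 1.9% and 14.9%, and the plan has no provision that would respond. These figures assume normal data, 25 independent effective observations per arm and equal SDs among the three graft arms; the clustered check at the plan's ICC agrees. The stated 57% and 0.65 SD are correct on their own inputs.

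For one outcome the unequal variance is built into the design: percent residual graft in SA-5. That figure assumes essentially no spread in Group 1. The case does not extend to the overall F-test or to Tukey's test elsewhere at moderate SD ratios.

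**What to change.** In section 12.4, under SA-1, and for any other contrast of Group 1 with pooled graft groups, prespecify an analysis in which both the between-subject and the residual variance may differ between Group 1 and Groups 2-4, with Satterthwaite or Kenward-Roger degrees of freedom. A Welch-type contrast on participant-level means is a simpler equivalent. A group-specific residual variance alone is not enough. Make this the default, so that it does not depend on a preliminary variance test.

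Under SA-5, compare percent residual graft among Groups 2-4 only, or with separate variances. Keep Tukey's test for the other pairwise comparisons.

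The cost is a short addition to the SAP, a slightly larger model for SA-1, and about one percentage point of power if the variances turn out equal. No change to the sample size or to data collection is needed.
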